## DATA HANDLING AND RECORD KEEPING

#### **Sources of Materials**

Research material obtained from participants will consist of a) data collected from the cognitive protocol administered during each cognitive testing session, b) brain images obtained during MRI and PET scans, c) blood, CSF, and stool samples collected during experimental sessions that will be assayed for specified peptides, neuroendocrine markers, and other measures. This study will be conducted in accordance with Good Clinical Practice (GCP) guidelines, as defined by the International Conference on Harmonisation (ICH) Guideline, Topic E6, the United States Code of Federal Regulations, Title 21, Part 50 (21CFR50) – Protection of Human Subjects and Part 56 – Institutional Review Boards (IRBs), HIPAA, State and Federal regulations and all other applicable local regulatory requirements and laws.

**Biomarker/APOE data handling:** Blood, CSF,DNA and stool samples will be handled in the following manner using a protocol developed by ADNI (Alzheimer's Disease Neuroimaging Initiative); a database will be created and used for the inventory of stored samples in conjunction with a bar code reading system. Bar code labels affixed to each sample vial will contain the following information: sample ID# (to preserve confidentiality), date of collection and processing, total initial volume collected, sample type (plasma, CSF, stool), volume, aliquot number, freezer, shelf, rack, box, location in the box. A bar code label will be used on the sample tracking form. There will be no link to participants' names. Samples will be catalogued and maintained at -80 °C.

**Neuroimaging data storage:** a) Image data collection and PHI: All imaging data will be uploaded and stored at the Radiology Informatics and Image Processing Laboratory (RIIPL) at Wake Forest, under the direction of co-investigator [name]. Only study number is entered into the scanning console interface at the time of the scan. Names are never used. As an extra check, when scans are uploaded, the images are quarantined while header fields are checked to ensure compliance with this policy, and

if in the rare case names are found they will be replaced with the study number and the site notified. b) Image management and access: Once uploaded and after initial quality and PHI checks, the images are inserted and catalogued into an auto-populating imaging database based on DICOM fields and metadata accompanying the upload. The images are backed up multiple times to prevent technical loss of data. At the scan console the exam is backed up to DVD and kept at the local site. The transferred images are maintained on a primary 40TB RAID6 server with nightly synchronization to a second server located in a separate building (both servers are housed in climate controlled specialized server rooms with secure physical and electronic access). The images are served back to the local sites or other authorized users via a secure web interface and the data access policy and granted access will be under the purview of the PI.

The following individuals involved in conducting this study may have access to individually identifiable private information about human participants: research team members and collaborators, federal oversight agencies including the National Institute of Aging, Food and Drug Administration (FDA), the Office for Human Research Protection (OHRP), and the Government Accountability Office (GAO); Institutional Review Boards from Wake Forest that oversees the safety and ethics of studies. All study personnel will be qualified by education, training, and experience to perform their respective task(s).

## **POTENTIAL RISKS AND BENEFITS**

# **Potential Risks and Protections Against Risks**

Risk Associated with Diet Interventions: The two diets utilized in this study, Modified Mediterranean -Ketogenic Diet (MMKD) and a modified American Heart Association Diet (AHAD), mainly differ based upon macronutrient ratios (carbohydrate and fat content). Participants on the MMKD will be asked to keep their daily carbohydrate consumption below 20 grams per day throughout the 4 month intervention and the amount of fat and protein may be variable. High fat foods (preferably low in saturated fats) will be added liberally to the diet plan. Throughout the duration of the study, participants on the MMKD will be encouraged to avoid low-carbohydrate store brought products and artificially sweetened beverages. Participants on the AHA will be encouraged to limit their amount of fat intake to <40 grams/day, while eating plentiful fruits, vegetables, and carbohydrates containing adequate fiber.

Participants on both interventions may lose weight depending on their baseline metabolic status. This is not an outcome measure of the intervention and will be carefully monitored as described below. We do not foresee a significant problem with safety based upon the common use of similar interventions in the general public and minimal safety issues reported in other literature using similar interventions.

Although symptomatic hypoglycemia (blood glucose <60 mg/dl) is rare with the MMKD, lowered blood glucose will be expected to occur as a result of the MMKD intervention, due to the restriction of carbohydrates. Some participants may experience fatigue or difficulty concentrating for the first few days on diet. However, if there is an adequate increase in circulating fatty acids/ketone bodies (as expected) for participants on the MMKD, these symptoms will resolve. Safety monitoring will occur at all scheduled study visits and education visits as well as during safety/adherence phone calls. At each study visit, participants will also be queried for any adverse events, changes in health status, or changes in medication. Blood chemistries will be obtained at regular intervals throughout the study. Participants and study partners will receive education regarding the symptoms of hypoglycemia, and instructed to consume their next scheduled meal/snack if they experience any symptoms. Although not anticipated, symptomatic hypoglycemia may occur in the first week of the MMKD intervention, as participant's preferred metabolic substrate is shifted from glucose to fatty acids/ketone bodies. Thus, additional safety checks will be scheduled during this time in concordance with the individual education visit day at week one. Decreased blood glucose is expected with the MMKD intervention, due to the change in metabolic fuel from glucose to fatty acids and ketone bodies. If study participants in either group become lethargic, dizzy, or have other significant symptoms medical history, blood

glucose/ketone levels, and Complete Metabolic Panel (CMP) results will be assessed by a study clinician to determine probable cause. Due to the higher fat/protein content of the MMKD dietary intervention there may be an increased risk for an exacerbation of gout in participants on the diet. Participants will be queried at baseline regarding any history of gout and informed of a potential exacerbation based on the MMKD intervention. Moreover, plasma uric acid levels will be monitored 4 times throughout the study at the screening visit and at weeks 8, 17 and 24. Study participants in the MMKD group may also experience dehydration and constipation. Each will be queried and monitored throughout the study at all interactions. Participants will be encouraged to drink plenty of water and report any significant symptoms to study personnel. MiraLAX may be suggested for participants with persistent constipation. The constraints of the MMKD specifically may lead to an inadequate intake of necessary vitamins and micronutrients. Thus, participants in the MMKD and AHAD groups will each receive the same daily multivitamin supplementation to ensure vital nutrients are consumed, especially in the MMKD group. Participants will be asked not to vigorously exercise during the first week for both interventions and not change their exercise pattern from their habitual pre-study pattern after the first week.

Risks Associated with Head Imaging using MRI: MRI is a non-invasive technique with no known side effects other than possible physical or psychological discomfort. No contrast agent is required. Participants with the following should not participate in MRI studies: metallic implants, such as prostheses, shrapnel, aneurysm clips, or persons with electronic implants, such as cardiac pacemakers. The magnetic field generated by the MRI machine can cause a displacement or malfunctioning of these devices and all participants will be thoroughly screened prior to entering the MRI room. Also, participants who have anxiety or claustrophobia will not be recommended to participate since the head must be placed fully inside the MRI scanner tube. In addition, fatigue and physical discomfort are possible. Earplugs are used in all participants due to the loud noise in the MRI scanning environment. These will not eliminate all sound, so that communication with the participant is still possible.

All participants will be rigorously screened by MRI personnel to be certain that they do not have any medical contraindications for MRI, which include metallic foreign bodies in the brain or eye or cardiac pacemaker. This safety screening is part of routine clinical practice at MRI centers and is performed before any participant is permitted to enter the scanning room. There is a slight risk of anxiety due to claustrophobia. Any participant who experiences anxiety when placed into the MR scanner will be removed from the scanner, offered reassurance by the MRI technician doing the scan, and offered the option of continuing or terminating the scan. If the participant decides that the anxiety associated with MRI is uncomfortable for them and they wish to terminate the scan, then the examination will be ended at that time. There will be no attempt to coerce participants to complete exams that they are uncomfortable with. Participants uncomfortable with MRI scans should preferably not be included in this study. Use of anxiolytic agents for completion of MRI scans is discouraged, but allowed at the discretion of study clinicians.

**Risks Associated with PET imaging:** PET imaging scans involve exposure to radiation. The amount of radiation exposure is considered low and comparable to everyday risks. For the three PET scans participants will receive about 3 Rem of exposure to radiation. This is the below the annual dose limit per patient of 5 Rem.

**Risks Associated with DEXA:** DEXA scans involve exposure to radiation. Although it can vary from person to person, whole-body radiation exposure from the two DEXA scans will be less than 6 mRem. The average annual exposure a person in the United States receives from natural background radiation is about 300 mRem. The risk of harm from this amount of radiation is low and no harmful health effects

are expected; however, risk of harmful effects may increase if the participant is exposed to more procedures that involve radiation within a short period of time.

**Risks Associated with Blood Draw:** Transient discomfort and bruising may occur when plasma is drawn, and there is a small risk of infection with any blood draw. In our experience, the discomfort associated with blood draws is usually minimal; every effort will be made to minimize any discomfort.

**Risks Associated with LP:** The risk for serious adverse events related to lumbar puncture (e.g., post-LP headache, infection, nerve root damage) is very low. Lidocaine may cause transient stinging and rare dermatitis. Rarely, patients may experience transient local pain at the site of the puncture or in the distribution of the sciatic nerve, if the nerve roots of the cauda equina are stimulated. Although very rare, it is possible that there may be an allergic reaction to the local anesthetic (lidocaine 1%) used for the LP. This reaction would cause swelling and a rash on the skin where the anesthetic was injected.

The LP is performed well below the termination point of the spinal cord. Because the nerve roots readily move aside from the spinal needle, the possibility of permanent nerve root damage is extremely remote. Post-LP headache has been commonly reported (~20% in young persons). The incidence of post-LP headache is a function of the diameter of the spinal needle rather than the amount of CSF drawn, and it may be related to age. The removal of up to 30 ml of CSF does not increase the risk of a post-LP headache. In order to minimize these risks even further, participants will be asked to hydrate well the day before the LP. Participants will remain supine for 30 minutes following the LP. Participants or authorized study partner will be contacted by the study nurse the day following the LP. They will also be told to avoid strenuous physical exercise and to call our clinic in the event of any discomfort. In the unlikely event of a post-LP headache that does not respond to conservative management, participants will return to the clinic and a trained anesthesiologist will perform a blood patch procedure. The blood-patch immediately terminates LP headaches.

**Other Risks:** Cognitive testing may produce frustration in some participants. If the participant appears distressed during cognitive testing, they will be comforted and encouraged. If the distress persists, testing may be discontinued. Stool collection does not pose any significant risks. Participants will be instructed on proper methods of collection and hygiene will be emphasized pre and post collection

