## **Objectives:**

- 1. Assess the safety and feasibility of a 4-month MMKD vs. the AHAD in adults with aMCI, and determine its effects on a key AD biomarker (CSF Aβ42 primary outcome), as well as on: cognition, cerebral metabolic rate of glucose utilization (CMRg) measured with F-FDG PET; brain ketone utilization assessed with C-acetoacetate PET; MRI measures of perfusion, hippocampal volume, default mode connectivity, and white matter integrity; and other CSF biomarkers (total tau, p-tau181).
- 2. Investigate response moderators: APOE genotype, amyloid PET positivity and metabolic status.
- 3. Investigate proposed mechanisms underlying MMKD effects, including: 1) neuronal activity and synaptic function (MRI, PET); 2) bioenergetic pathways (mitochondrial function assays, plasma neural-derived exosome markers); 3) epigenetic analyses; 4) CSF/blood multi-omic panels (proteomics, metabolomics, lipidomics, transcriptomics).

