# Storage and Distribution of Study Supplements

The multivitamins and olive oil provided to participants in the study diet groups will be stored within the Sticht Center at Wake Forest University School of Medicine. The supplements will be kept within a locked area on the first floor Kulynych Research Center. Participants on the MMKD will receive olive oil as needed at their in-person study visits. The olive oil will be used as an added fat source. All participants in the diet study will receive Centrum Silver multivitamin tablets at baseline to take throughout the study.

**Blinding:** Although it is not possible for participants and the dietitian to be blinded to the study diet, all study personnel involved in performing cognitive testing or other outcome procedures or data analysis will be blinded. Participants will receive equal attention and instruction regarding their diets, and must expend similar amounts of effort to comply with dietary requirements. It will also be emphasized to participants that both diets may reasonably be expected to provide health benefits.

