**Phone Sessions**: Each participant will have a phone session in addition to diet education with the study dietitian 3-4 days after starting the diet and again in week 2. These session will allow the participants and caregivers to ask questions and receive support as needed. Phone sessions will also occur in weeks 9-11 and 13-16, and may be increased in frequency as needed to optimize compliance.

Note: Data will be recorded at Diet Education Visits, including capillary glucose/ketone testing, weight, adverse events, diet compliance, and nutritional intake.

Table. 2. Schedule of Study Visits and Procedures

Clinic Visit #	1	2	3	4	5	6	7	8	9	10	11	12	13	14	15	16	17	18	19
Visit Week	-12		Baseline			1	2	3	4	5	6	7	8	12		17		20	24
Visit Name	Screen	Pre Cog	Pre LP	Pre dtPET	Pre amyPET	Edu	Mid Cog	Edu	Post Cog	Post LP	Post dtPET	Interm. F/U	F/U Visit						
Informed Consent	Χ																		
Demographics	Χ																		
Medical History	Χ																		
Phys/Neuro Exam	Χ																		
Screen Cognitive Battery	Χ																		
Concomitant Meds	Χ												Х		Х				Х
Resting Metabolic Rate		Х													Х				
Vital Signs	Χ	Х	Х	Х	Х								Χ		Х	Х	Х	Χ	Χ
Diet Cognitive Battery		Х											Χ		Х				Χ
Weight	Χ	Х			Х	Χ	Х	Χ	Χ	Х	Х	Χ	Χ	Χ	Х			Х	Х
Capillary Gluc/KB	Χ				Х	Χ	Х	Х	Χ	Х	Х	Χ	Χ	Х	Х			Х	Х
Blood Draw:	Χ	Х	Х						Χ				Χ	Χ	Χ	Х			Χ
APOE Genotyping		Х																	
Clinical / Safety Labs	Χ												Χ		Х				Χ
Metabolic Outcomes			Х						Χ				Х	Х	Х				Χ
Mito, Epign & Exo		Х													Х				
Blood Banking		Х	Х										Χ		Х	Х			Χ
Stool Banking		Х											Χ		Х				Χ
CSF Banking			Х													Х			
LP			Х													Х			
DEXA Scan		Х													Х				
MRI		Х													Х				
dtPET				Х													Х		
amyPET					Х														
Diet Edu. / Compliance					Х	Χ	Х	Χ	Χ	Х	Х	Χ	Χ	Х					
Food Diary		Х				Х	Х	Х	Χ	Х	Х	Χ	Χ	Х	Х				
Compliance Call						Х	Х						Χ	Х					
Adverse Events		Х	Х	Х	Х	Х	Х	Х	Χ	Х	Х	Χ	Χ	Х	Х	Х	Х	Х	Х
Safety Phone Check			Х													Х			
Sleep Battery/Monitor.		Х											Х		Χ				Χ

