# Data and Safety Monitoring

The principal investigator will be responsible for the overall monitoring of the data and safety of study participants, with assistance by members of the study staff, and the Data and Safety Monitoring Board (DSMB), which will be responsible for monitoring the safety of research participants. The DSMB will consist of a neurologist and statistician from another institution who have been approved by the study sponsor (NIA) and by the Wake Forest IRB. Information regarding serious adverse events (SAEs) will be presented to the DSMB every six months, collated in A-B format by an independent statistician. The DSMB may recommend stopping the trial before its planned conclusion if convincing evidence is observed of a treatment difference in adverse events. Recommendations of the DSMB after each review will be presented to the study PI and IRB. Participants will be screened at the beginning of the study and will have their clinical labs and other results (i.e. neuroimaging) monitored carefully at each study visit.

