# Reporting of Unanticipated Problems, Adverse Events or Deviations

Any unanticipated problems, serious and unexpected adverse events, deviations or protocol changes will be promptly reported by the principal investigator or designated member of the research team to the IRB and sponsor or appropriate government agency if appropriate.

All participants will be evaluated for adverse events (AEs) during each study visit. All AEs will be recorded on an adverse event case report form. Based on the nature of the AE, study physicians will determine the severity of the event and the association with the study. All SAEs will be recorded on an IRB "Serious Adverse Event" case report form. SAE are defined as events that are (1) life-threatening or fatal; (2) result in severe or permanent disability; or (3) require hospitalization, other than brief emergent care for non-life threatening conditions. All SAEs will be reported to the IRB within seven calendar days of the investigator or other members of the study team becoming aware of the event. SAEs will be followed until resolution, even if study participation has been terminated.

The "severity" of events will be graded according to the following guidelines:

- 1. *Mild:* The patient is aware of, but can easily tolerate, the event;
- **2.** *Moderate:* The discomfort of the event is severe enough to interfere with some usual activities:
- 3. Severe: The patient is incapacitated, and unable to perform most or all usual activities.

The "study relatedness" will be assigned according to the following guidelines:

- 1. **Definitely Related:** The reaction follows a reasonable temporal sequence and is known to be an effect of the medication or procedure;
- **2. Probably Related:** The reaction follows a reasonable temporal sequence with reasonable suspicion that the study medication or procedure caused or contributed to the event;
- **3. Possibly Related:** The reaction follows a reasonable temporal sequence, and current medical knowledge does not preclude a relationship between the medication or procedure and the event:
- **4. Unlikely:** Current medical knowledge precludes a causal relationship between the medication or procedure and the event;
- **5. Definitely Unrelated:** The cause of the reaction is known to be other than the medication or procedure.

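### The targeted query on dehydration and constipation is written for the MMKD group, and no matching prompted question is specified for AHAD, so counts of these symptoms may not be comparable between arms.

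*Combined protocol and SAP*

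**What the plan says.** All references are to the combined protocol and SAP.

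- **Targeted query** (Potential Risks and Protections Against Risks, diet interventions): "Study participants in the MMKD group may also experience dehydration and constipation. Each will be queried and monitored throughout the study at all interactions".
- **General query** (same section): "At each study visit, participants will also be queried for any adverse events, changes in health status, or changes in medication". The adverse-event reporting section adds: "All participants will be evaluated for adverse events (AEs) during each study visit". Neither is limited to an arm.
- **Contacts** (same risk section): "Safety monitoring will occur at all scheduled study visits and education visits as well as during safety/adherence phone calls". The note under Phone Sessions adds: "Data will be recorded at Diet Education Visits, including capillary glucose/ketone testing, weight, adverse events, diet compliance, and nutritional intake".
- **Who asks**: the In-Person Diet Education Sessions and Diet Educational Study Visits paragraphs have the study dietitian leading these contacts. The Blinding paragraph accepts that neither the dietitian nor the participants can be blinded.
- **Use of the data**: Objective 1 begins "Assess the safety and feasibility of a 4-month MMKD vs. the AHAD in adults with aMCI". Data and Safety Monitoring says: "The DSMB may recommend stopping the trial before its planned conclusion if convincing evidence is observed of a treatment difference in adverse events". It also says that the information given to the board every six months concerns serious adverse events.
- **Analysis**: Statistical Analysis and Power describes no adverse-event comparison.

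**The concern.** A symptom that is asked about by name at every contact is generally recorded more often than one that the participant must volunteer in answer to a general question. If one arm gets the named question and the other does not, recorded counts differ even when true rates are the same.

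Constipation and dehydration are harms that the protocol itself attributes to the MMKD, so they are where a fair comparison with AHAD matters most. The Summary of supporting research says that the trial's safety data will inform a Phase III design. If prompting is unequal, an observed excess cannot be divided into a real part and a part due to asking. No later analysis can recover AHAD symptoms that were never asked about.

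**Working it through.** **Step 1: the wording.** The plan gives no figure on this point, so the first check sets the passages side by side.

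| Item in the diet-risk section | Arm as written |
|---|---|
| Lethargy, dizziness, other significant symptoms | either group |
| Daily multivitamin | both groups named |
| Exercise restriction | both interventions |
| Dehydration and constipation query | only MMKD named |

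Where this section means both arms, it usually says so. For the dehydration and constipation query it does not. *Each* can refer to each symptom or to each MMKD participant. On the first reading the arm is left open; on the second it is MMKD. On neither reading is the prompt assigned to AHAD. What AHAD participants are certain to get is the general adverse-event query.

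**Step 2: equal contact is not equal questioning.** The visits, calls and adverse-event recording are common to both arms. The Blinding paragraph's assurance, "Participants will receive equal attention and instruction regarding their diets", concerns diet teaching. None of this fixes the wording of the symptom question.

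**Step 3: size if prompting were unequal.** This is an illustration, not an estimate.

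Inputs:
- n = 60 per arm (Sample Size section).
- True incidence 10%, 20% or 30%, the same in both arms (assumed).
- Capture 90% when prompted, and 70%, 50% or 30% with the general query only (assumed).

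Formulas:
- Expected recorded cases = 60 × incidence × capture. At 30% incidence: 60 × 0.30 × 0.90 = 16.2 with prompting, and 60 × 0.30 × 0.50 = 9.0 without.
- Apparent risk ratio = 0.90 / unprompted capture = 1.29, 1.80 or 3.00.
- Probability of two-sided Fisher p ≤ 0.05, by summing the binomial probabilities of all rejecting tables.

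| True incidence | Prompted cases | Unprompted cases (70 / 50 / 30% capture) | P(p ≤ 0.05) (70 / 50 / 30% capture) | Both arms prompted |
|---|---|---|---|---|
| 10% | 5.4 | 4.2 / 3.0 / 1.8 | 3% / 6% / 14% | 2% |
| 20% | 10.8 | 8.4 / 6.0 / 3.6 | 6% / 17% / 42% | 3% |
| 30% | 16.2 | 12.6 / 9.0 / 5.4 | 8% / 28% / 66% | 3% |

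The effect is negligible when incidence is low and unprompted capture is good. It is large when symptoms are common and seldom volunteered.

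**The case against.** The strongest reply is that the protocol nowhere limits the prompt to MMKD. The nearest antecedent of *Each* is the pair of symptoms, and the sentences that follow, on drinking water and reporting symptoms, speak of participants without naming an arm. The same section also takes several measures because of MMKD risks and applies them more widely: both arms receive the multivitamin, and uric acid is first measured at screening, before randomisation. Naming MMKD as the source of a risk therefore does not prove that only MMKD participants are asked. This stands. A reader might infer an expressly MMKD-only query, but the text supports only an unresolved ambiguity.

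A reader might also infer that the additional first-week safety checks are confined to MMKD. They are motivated by hypoglycaemia on that diet, but they are tied to the week-one education visit, which is held for both diets, and every participant has a call 3-4 days after starting. The documents do not support that inference.

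The consequences are also limited. The board's reports are described as serious adverse events, which would rarely include these symptoms, although the stopping sentence refers to adverse events generally. No adverse-event test is planned, so the Fisher figures describe an analysis that a reader of the results might do, not one in the plan. Every rate in them is assumed, and they presuppose unequal prompting.

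What the reply does not supply is any passage that gives AHAD the same prompted question.

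**Conclusion.** The point holds as a gap in specification. The named-symptom query is attached to MMKD risks, AHAD is assured only a general query, and unblinded staff record the answers. Staff following the text could therefore prompt one arm only.

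If they did, an MMKD excess of constipation or dehydration would be partly or wholly due to asking. It would be wrong to conclude that any excess would come only from asking: the protocol expects these symptoms as real effects of the MMKD, and the difficulty is that real and artefactual parts could not be separated.

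The damage is confined to the comparison of these non-serious symptoms under Objective 1. CSF Aβ42 is untouched, and any influence on a stopping recommendation is likely small. Under the assumed rates, the chance of a nominally significant difference with no true difference runs from about 3% to 66%, against 2-3% with equal prompting. The width of that range reflects how little the documents say about incidence and capture. This is a worthwhile, inexpensive improvement, and it has to be made before the data are collected.

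**What to change.** Amend the diet-risk text in Potential Risks and Protections Against Risks to say that dehydration and constipation are asked about in the same words, at the same visits and calls, in both arms. A short fixed checklist would serve, and could also carry the other symptoms that the section names. Add a field to the adverse-event form marking each event as solicited or spontaneously reported. Add a sentence to Statistical Analysis and Power stating that arms will be compared on the solicited items, with spontaneous reports shown separately.

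The contacts already exist in both arms, so no visits are added and neither diet nor clinical management changes. The cost is a few minutes per contact and more mild events recorded in AHAD. If equal questioning was always intended, a sentence saying so removes the ambiguity; the solicited/spontaneous flag would still be useful.
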